 - If you have difficulty speaking or raising your arm or leg, think of 3 new positive opportunities that this difficulty provides.
- **Unpredictability:** a mindful view of the future acknowledges its ultimate unpredictability, as is the course of the participant’s disability. Such unpredictability opens up the possibilities for a more positive perception of the future than had been conceived. For example:
 - Find 3 possible reasons that explain why a certain event might occur, and then propose 3 reasons that it might not. For each of those reasons, describe the way in which it is both positive and negative.
- **Sense Making:** Disability and symptoms tend to be perceived as something that stays unchanging. However, it is unlikely that all symptoms are always present at the same

intensity or at the same level of impairment. Reflecting about symptoms and your ability to do things that are important to you allows for understanding their variability, and making sense of this can help develop an understanding that there are often many reasons for their variability. Once we can identify even a few reasons, feelings of increased control and awareness follow. One example of this is:

- Is today a better day than yesterday? What about compared to last week? In what ways is it better or worse? Can you think of 3 reasons why?
- **Novelty seeking and novelty producing:** The attitude of paying attention to new elements requires an open and curious orientation toward the world and towards oneself. Novelty producing actively creates new categories of thinking rather than relying on previously constructed categories and distinctions about the world (Langer, 1989). Novelty seeking is also related to the concept of flexibility, or using feedback from the environment to make any responsive adaptations to one's thinking and behavior. These attitudes may be improved in an effort to be more mindful. Examples of exercises with this purpose may be:
 - Imagine taking a new route to get from your house to any places to which you go very regularly. What new reactions occur to you?
 - What are five ways you could change your bathroom – even slightly - in order for it to make it easier for you to get in and out of the shower?

4.1 Preface

The incidence of depression and anxiety is much higher in stroke survivors and their caregivers compared to age-matched peers. Previous work suggests that mindfulness delivered in an online format is promising for both individuals with neurological disorders and caregivers to improve quality of life and psychological well-being. The potential application of a non-meditative Langerian mindfulness intervention, however, has never been explored.

This statistical analysis plan (SAP) will give more detailed descriptions of the endpoints in the study and the corresponding analyses.

5. Study Objectives and Endpoints

5.1 Study Objectives

1. To pilot test the online mindfulness program with potential users to evaluate the acceptability, ease-of-use, and satisfaction.
2. To estimate the potential impact on quality of life, anxiety, depression and sleep quality in the short term.
3. To obtain a final version suitable for individuals who have had a stroke with a wide range of impairments and their caregivers.

5.2 Endpoints

Stroke survivors:

- Change in Stroke Impact Scale (SIS): quality of life and impact of stroke (primary, post-intervention)
- Change in Hospital Anxiety and Depression Scale (HADS): anxiety and depression (secondary, post-intervention).
- Change in NIH Perceived Stress Survey (NIH PSS): perceived stress (secondary, post-intervention).
- Change in Single-Item Sleep Quality Scale: Sleep quality (secondary, post-intervention).
- Post-Study System Usability Questionnaire (PSSUQ): Usability of the online platform used to host the intervention (secondary, post-intervention).

Caregivers:

- Change in World Health Organization Quality of Life-BREF (WHOQOL-BREF): quality of life (secondary, post-intervention).
- Change in Zarit Burden Interview: perceived burden (secondary, post-intervention).
- Change in Hospital Anxiety and Depression Scale (HADS): anxiety and depression (secondary, post-intervention).
- Change in NIH Perceived Stress Survey: perceived stress (secondary, post-intervention).
- Change in Single-Item Sleep Quality Scale: Sleep quality (secondary, post-intervention).
- Post-Study System Usability Questionnaire (PSSUQ)

All outcome measures are administered at 3 time points: pre-intervention, within 48 hours of the end of the intervention and at 1-month follow-up (+/- 1 week). All outcome measures are administered via REDCap. A qualitative semi-structured interview is also conducted post-intervention to capture satisfaction and usability of the mindfulness intervention.

Safety outcomes

[figure not shown]
Adverse events are reported at each meeting. Participants are asked about any change in their medical status or hospitalization, since the last meeting.

6. Study Methods

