6.3 Study Assessments

Table 1. Outcome measures at each time point

Visit	Baseline	Post-intervention	Follow-up
Target day of visit	1	22	52
Protocol assessment time windows (days)	1	± 2	± 7
Participant characteristics	x		
SIS*	x	x	x
HADS	x	x	x
NIH PSS	x	x	x
Sleep Quality	x	x	x
WHOQOL-BREF†	x	x	x
Zarit Burden Inventory†	x	x	x
PSSUQ		x	
Qualitative semi-structured interview		x	
Adverse event monitoring	x	x	x

* Stroke survivors only

† Caregivers only

The SIS 3.0 includes 59 items organized in 8 domains about the impact of stroke on health and life. Each question is scored from 1 (severe difficulty) to 5 (no difficulty) and each domain score is normalized. Higher scores indicate lower perceived impact of stroke. Participants also rated their perceived recovery on a sliding scale from 1 (no recovery) to 100 (full recovery).

The HADS is a 14-item scale with 7 items each for anxiety and depression subscales. Each item is scored from 0 to 3, with higher scores indicating higher anxiety or depressive symptoms.

The NIH PSS includes 10 items about the occurrence of life stressors scored from 0 (never) to 4 (very often). Higher scores indicate higher perceived stress.

The Single-item Sleep Quality includes an 11-point visual analogue scale about sleep quality in the past week (0: poor, 10: excellent sleep quality).

The WHOQOL-BREF comprises 26 questions from 4 domains about health and well-being. The scores

are normalized, and higher scores indicate better perceived health and well-being. The Zarit Burden Interview includes 22 questions about caregiver burden rated from 0 (never) to 4 (nearly always). Higher scores indicate higher perceived burden.

The adapted PSSUQ consists of 5 questions on perceived satisfaction with the website. Each question is scored on a 7-point Likert scale from 1 (Strongly Agree) to 7 (Strongly Disagree). Higher scores indicate lower usability.

7. Sample Size

A convenience sample of 10 stroke survivors is targeted to capture the relevance, feasibility and usability of the Mindfulness Program and to obtain data saturation and richness on the qualitative semi-structured interviews. This study is not powered to detect differences in quality of life or psychological well-being.

8. General Analysis Considerations

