8.2.2 Safety Population

- All participants who received the intervention but excluding participants who drop out prior to receiving any treatment.

All outcomes will be presented using descriptive statistics; normally distributed data by the mean and standard deviation (SD) and skewed distributions by the median and interquartile range (IQR). Binary and categorical variables will be presented using counts and percentages. JASP version 0.14.1. will be used for all statistical analysis.

The subsections below will describe analyses in addition to the descriptive statistics.

The results of the adapted PSSUQ will be averaged for each group. For each group, differences prior to, after the mindfulness program and at 1-month follow-up will be assessed using a repeated measure analysis of variance (ANOVA). If data normality is violated, data will be transformed, or non-parametric statistics will be substituted. The semi-structured interview will be transcribed verbatim and analyzed independently using thematic content analysis by 2 members of the research team to identify codes, themes and overarching categories, using the Braun & Clarke six-step framework for inductive thematic analysis.

9. Summary of Study Data

Participant characteristics and the mean scores for each self-reported measure will be summarized in a table format.

A figure will be created with individual data and mean data for each outcome measure.

All continuous variables will be summarized using the following descriptive statistics: n (sample size), mean and standard deviation. The percentages (based on the sample size) of observed levels will be reported for all categorical measures.

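### The SAP's only primary endpoint, change in SIS, does not say which SIS score or scores it means, and the planned ANOVA has no baseline-to-post contrast, confidence interval or multiplicity rule

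*SAP*

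**What the plan says.** - **Primary endpoint.** SAP 5.2 lists "Change in Stroke Impact Scale (SIS): quality of life and impact of stroke (primary, post-intervention". Every other endpoint there is labelled secondary, except the caregiver PSSUQ, which has no label. The Protocol names no primary endpoint and refers to the SAP for the analysis.
- **Scoring.** SAP 6.3: "The SIS 3.0 includes 59 items organized in 8 domains about the impact of stroke on health and life". Normalisation is done domain by domain. The same paragraph adds "Participants also rated their perceived recovery on a sliding scale from 1 (no recovery) to 100 (full recovery". No total, composite or lead domain is described, and the recovery rating is placed neither inside nor outside the primary.
- **Test.** The analysis text after SAP 8.2.2: "For each group, differences prior to, after the mindfulness program and at 1-month follow-up will be assessed using a repeated measure analysis of variance", with a transformation or a non-parametric method if normality fails. The text names no SIS score, significance level, contrast between two time points, confidence interval or multiplicity rule.
- **Display.** SAP 9 plans a table of mean scores for each self-reported measure and says "A figure will be created with individual data and mean data for each outcome measure".
- **Purpose and size.** Objective 2 in SAP 5.1 is "To estimate the potential impact on quality of life, anxiety, depression and sleep quality in the short term". SAP 7 says "A convenience sample of 10 stroke survivors is targeted to capture the relevance, feasibility and usability of the Mindfulness Program" and "This study is not powered to detect differences in quality of life or psychological well-being".

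**The concern.** A primary endpoint needs a variable, a time point and a comparison. SAP 5.2 supplies the time point. The variable is left open, because SAP 6.3 offers eight domain scores and possibly a ninth, with no rule for combining or ranking them. The comparison is also open. A repeated measures ANOVA over three visits tests for any difference among baseline, post-intervention and follow-up, whereas the endpoint is a change at post-intervention only.

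Two analysts following the SAP could therefore report different primary results. One might run the ANOVA on every SIS score and produce several unadjusted tests under a single primary label. Another might choose one score after seeing the data. The Protocol (Phase 2, data collection) says these measures are meant to inform a later intervention study, including through a preliminary effect. An SIS estimate chosen because it looked favourable would carry its bias into that planning, whether or not a p-value is quoted.

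**Working it through.** The SAP gives no figure to reproduce: the target of 10 has no significance level, power, effect size or SD behind it. The numbers below illustrate what the gap permits.

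**Inputs**
- n = 10 stroke survivors (SAP 7). The Protocol allows 5–10.
- k = 8 domain scores, or 9 with the recovery rating (SAP 6.3).
- Assumed: no true change; each score tested at two-sided 0.05 (the SAP states no level); equal SDs of change; a common correlation r between changes in the scores, from 0 to 0.9 because the documents give none.

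**1. Chance of at least one false positive**

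Independent scores, either direction: 1 − 0.95^8 = 0.337 and 1 − 0.95^9 = 0.370.

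Independent scores, improvement only (2.5% per score): 1 − 0.975^8 = 0.183 and 1 − 0.975^9 = 0.204.

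Correlated scores were simulated with a paired t-test on baseline-to-post change at n = 10:

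| r | Either direction, k = 8 / 9 | Improvement only, k = 8 / 9 |
|---|---|---|
| 0 | 34% / 37% | 18% / 20% |
| 0.5 | 26% / 28% | 13% / 14% |
| 0.7 | 21% / 22% | 10% / 11% |
| 0.9 | 13% / 14% | 6% / 7% |
| One named score | 5% | 2.5% |

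The test the SAP actually names, an ANOVA over three time points with spherical errors, gives almost the same two-sided rates: 34% / 37% at r = 0, 27% / 29% at 0.5 and 21% / 22% at 0.7.

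**2. Worst-case selection without any test**

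If only the score with the largest mean improvement is headlined, its expected apparent improvement, in SD of change, is E[max of k standard normals] × √(1 − r) / √n. E[max] is 1.424 for k = 8 and 1.485 for k = 9.

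- r = 0: 1.424/√10 = 0.45; 1.485/√10 = 0.47
- r = 0.5: 0.32; 0.33
- r = 0.7: 0.25; 0.26
- r = 0.9: 0.14; 0.15

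One pre-named score gives 0 on average. At n = 5 these values rise by √2, for example 0.45 × 1.414 = 0.64 for k = 8 at r = 0.

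**3. Precision of one score**

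The 95% CI half-width for one mean change at n = 10 is t(0.975, 9)/√10 = 2.262/3.162 = 0.72 SD. The selection effect is smaller than this, but it always favours improvement, whereas sampling error has no preferred direction.

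**The case against.** The strongest reply is that this is an openly exploratory pilot. It is non-randomised, it sets no success criterion, and the only hypothesis in the Protocol concerns acceptance and ease of use. A family-wise error rate presumes a significance level and a claim of success on any domain, and the documents contain neither. SAP 9 also plans to show means and individual data for each measure, which limits hidden selection.

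Much of this stands, and it rules out three stronger readings that a reader might infer:

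- **That the primary is eight or nine tests.** The SAP never says that each domain is primary or will be tested, or that the recovery rating belongs to the primary. SAP 6.3 describes how the instrument is scored, and the planned display for each measure could mean one SIS value or several. The number of primary tests is undefined, not fixed at eight or nine.
- **That lack of power is an error.** SAP 7 discloses it, and objective 2 asks only for an estimate. Measuring the SIS is within the objectives.
- **That a biased headline is to be expected.** The 0.14–0.47 SD range requires someone to feature only the best score. It is a ceiling under simple assumptions, not a forecast. The two-sided rates also count apparent worsening, so the improvement-only column is closer to the harm at issue.

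The reply does not remove the core point. The SAP chose both a primary label and an inferential test, so p-values for the SIS are likely. The planned table and figure do not say that the SIS will be shown by domain or which score is the main one.

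**Conclusion.** The point holds as a gap in definition. SAP 5.2 fixes when the primary endpoint is measured but not which SIS score it is. The ANOVA does not isolate the change from baseline to post-intervention, gives no interval and has no rule for several scores.

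If every score were tested, the chance of at least one false improvement would be roughly 6–20% over the assumed correlation range, against 2.5% for one named score. The two-sided range is 13–37%, against 5%. These figures rest on n = 10, no true change, an assumed two-sided 0.05, equal SDs and equal correlation. The conclusion that the primary result is not uniquely defined needs none of those assumptions. It should be settled before the outcome data are analysed, and it does not call the design or the sample size into question.

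**What to change.** In SAP 5.2 and the analysis text, take one of two routes:

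1. **Preferred, in line with objective 2.** Report the mean change from baseline to post-intervention with a 95% CI for each of the eight SIS domains and the recovery rating. Display them by domain and label them exploratory. State that no efficacy claim will rest on a single p-value or a single interval that excludes zero.
2. **If an SIS primary is kept for testing.** Before the data are analysed, name one SIS score and the baseline-to-post-intervention contrast, and make the other SIS scores secondary. Naming the score alone is not enough, because the ANOVA as written does not test that contrast.

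Whether to make usability primary instead is the sponsor's choice and is not needed to close this gap.

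The cost is wording only, with no new data collection. The first route gives up a headline SIS p-value; under the second, the other SIS scores cannot be presented as primary. If any outcome data have already been seen, the change should be dated and disclosed as made after that point.

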who may not be mobile enough to attend face-to-face classes in a rehabilitation, hospital or community settings or living in a remote area to participate.

Phase 1 – Development of the online mindfulness program

The first phase of the study focuses on the development of a three-week online mindfulness program, with distinct modules for individuals who have had a stroke and for caregivers. The modules are based on a mindfulness program initially developed for individuals with ALS and caregivers (Pagnini et al., 2017). To ensure suitability and relevance for individuals with stroke with a wide range of impairments and disabilities, a group of experts consisting of experienced therapists, stroke rehabilitation researchers, stroke survivors and mindfulness experts revised and adapted the content of the program. Stroke-specific exercises were also incorporated into the program to ensure the exercises *made sense* from stroke survivors' and caregivers' points of view. The purpose of the online mindfulness program is to increase participants' mindfulness and improve psychological state. The mindfulness program also encourages stroke survivors to change their beliefs about their disability. For caregivers, the program is designed to help caregivers better accept themselves and the individual who has sustained a stroke as autonomous and unique human beings rather than as a caregiver and a stroke survivor.

The online mindfulness will be hosted on the USC Biokinesiology and Physical Therapy continuing education platform named Desire2learn. Desire2learn is a user-friendly, commonly used platform in higher education. The content of the program will be accessible via a computer or a smartphone. Additional features of this platform include a discussion forum, exercise submission, ability to contact a member of the research team to ask questions about the program or to report any adverse events, and flexibility and ease to modify the content for the instructors.

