and 4) Single-Item Sleep Quality Scale (Snyder et al., 2018). For caregivers, quality of life, anxiety and depression, perceived burden, perceived stress and sleep quality will be assessed: 1) World Health Organization Quality of Life-BREF (WHOQOL-BREF; World Health Organization, 1998), 2) HADS, 3) Zarit Burden Interview (Zarit et al., 1980), 4) NIH Perceived Stress Survey, and 5) Single-Item Sleep Quality Scale. All outcome measures will be administered remotely using the REDCap platform. Specifically, a link to access the REDCap questionnaires will be sent by emails. With the guidance from the researcher, participants will complete each self-reported questionnaire.

For each week of the online mindfulness program (3 weeks total), participants will be instructed to connect to the platform and accomplish daily exercises a minimum of 5 days per week to optimize participation. Participants will be able to call or contact via the platform a member of the research team at any time to ask questions or report difficulties. Any difficulty reported will be recorded. At the end of the 3-week program, another Zoom meeting will be conducted with each participant to administer the self-reported questionnaires and conduct a semi-structured interview. In addition to the patient-reported outcome measures administered after the end of the program, an adapted version of the Post-Study System Usability Questionnaire (PSSUQ), will be administered to assess the usability of the mindfulness program. The adapted version of the PSSUQ consists of 5 questions on user's perceived satisfaction of a website or software. Each question is scored on a 7-point Likert scale ranging from Strongly Agree to Strongly Disagree. In a semi-structured interview lasting up to 30 minutes, participants will also be asked to provide feedback about technical issues (e.g., whether the website is fully accessible), program content and their feelings, beliefs, reactions and adherence to the program. In particular, the clarity of the lectures and other exercise communications, the duration of the program and the perception of the utility of the exercises will be verified. The interview will be video recorded.

Data analysis: See SAP

Phase 3 – Modifications to obtain a final version

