All information collected during this study will be coded in order to assure confidentiality and each participant will be assigned a random unique identification code. Once transcribed and verified for accuracy, the recordings of the semi-structured interviews will be destroyed. Electronic data will be stored on a secured drive and access to the drive will be password protected. Data will be stored for a period of seven years following the end of the study, after which, they will be destroyed. Only the members of the research team will have access to the data. The data identifier will be stored in a different location than the data generated during the study.

Potential risks and procedures for minimizing risks

The risks associated with this study are minimal and there are no expected adverse events. Risks include surveys or interview questions that may make participants feel uneasy or embarrassed, and a breach of confidentiality. During any self-reported or interview question, participants will be allowed to skip or stop answering any questions they wish not to. The HIPAA compliant REDCap platform will be used to obtain informed consent and collect all patient-reported outcomes (coded surveys). No identifier will be collected in REDCap. Study investigators will protect data against the privacy by storing data in locked cabinet, in password protected computers and files, and by using coded identifiers. If a participant scores over 11/21 on the HADS scale for depression and anxiety or if they experience any inconvenience during the study, they will be directed to their primary family physician to ensure they are receiving proper referral to mental health care.

Plan to disseminate findings

It is anticipated that the results from this study will be disseminated in a peer-review publication and at local, national and/or international conferences. To facilitate the knowledge

translation for students doing stroke research, the results will be presented at the Biokinesiology and Physical Therapy Division seminars at the University of Southern California.

References

Alexander, C. N., Langer, E. J., Newman, R. I., Chandler, H. M., & Davies, J. L. (1989). Transcendental meditation, mindfulness, and longevity: an experimental study with the elderly. *Journal of Personality and Social Psychology*. <https://doi.org/10.1037/0022-3514.57.6.950>

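### The one prompted adverse-event question does not ask about the risks the protocol names, and the SAP has no rule bringing other reports of them into the safety results

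*SAP*

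**What the plan says.** Under Safety outcomes, SAP 5.2 says "Adverse events are reported at each meeting" and then "Participants are asked about any change in their medical status or hospitalization, since the last meeting". Table 1 in SAP 6.3 marks adverse-event monitoring at baseline, post-intervention (Day 22) and follow-up (Day 52).

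The protocol's section on potential risks states "The risks associated with this study are minimal and there are no expected adverse events", and continues "Risks include surveys or interview questions that may make participants feel uneasy or embarrassed, and a breach of confidentiality". It also says that a HADS score over 11/21, or any inconvenience, leads to referral to the participant's physician.

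The protocol has open routes for reports. Phase 1 lists among the platform's features the "ability to contact a member of the research team to ask questions about the program or to report any adverse events". In Phase 2 participants may "call or contact via the platform a member of the research team at any time to ask questions or report difficulties", and "Any difficulty reported will be recorded". The closing interview covers feelings and reactions as well as technical matters.

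SAP 8.2.2 defines a safety population. The general text that follows says all outcomes will be described, with counts and percentages for categorical variables. No adverse-event summary is specified, and SAP section 10 lists one figure (the flow chart) and one table (the assessment schedule).

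**The concern.** The protocol considers what could go wrong and names two things: discomfort from being questioned, and loss of privacy. The safety question asks about something else, namely health changes and hospital stays. A participant who was upset or had a privacy worry could answer no to it truthfully. Embarrassment in particular is something people may not raise unless asked.

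The documents do collect material that bears on distress, but each source has another stated purpose. HADS is a secondary efficacy endpoint, the interview serves satisfaction and usability, and difficulties are simply recorded. None is linked to the safety population.

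The pilot is meant to guide a later intervention study. If it reports no adverse events, the later team may take that as evidence on the named risks, when most of that evidence would be the absence of spontaneous complaint.

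**Working it through.** No safety rate, threshold or precision target is given, so there is no figure to reproduce. The check is whether each harm or signal is asked about directly, and whether any text carries it into the safety results.

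1. **Unease or embarrassment from questions** (Protocol, potential risks). Not named in the SAP 5.2 prompt. It could surface through the unrestricted reporting sentence in SAP 5.2, the platform, a call to the team, or the interview. The first three depend on the participant raising it. The interview invites it, but SAP 8 sends interviews to thematic analysis, not to a count.

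2. **Breach of confidentiality** (Protocol, potential risks). Not named in the prompt and not among the interview topics listed in Phase 2. It depends on an unprompted report or on the team finding it.

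3. **Recorded difficulties** (Protocol, Phase 2). They are recorded, but no text says which of them count as adverse events.

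4. **HADS over the cut, or inconvenience, leading to referral** (Protocol, potential risks). SAP 6.3 describes two subscales of 7 items scored 0 to 3, so the maximum per subscale is 7 × 3 = 21. The cut out of 21 therefore works at subscale level. HADS is taken in both groups at all three time points, so the data for a count already exist. SAP 5.2 lists HADS only as a secondary change endpoint, and no text counts referrals as a safety result.

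5. **Timing.** SAP 5.2 ties reporting to meetings. Table 1 requires monitoring at Day 52, which is 52 − 22 = 30 days after the post-intervention visit. The protocol describes an opening online meeting, and at the end of the program "another Zoom meeting will be conducted with each participant to administer the self-reported questionnaires and conduct a semi-structured interview". It describes no 1-month meeting. Questionnaires are completed through an emailed link with a researcher's guidance, which may imply contact then. This is silence, not contradiction.

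6. **Who is counted.** The full analysis population in SAP 8.2.1 is completers; the safety population in SAP 8.2.2 is everyone treated. The documents describe no exit contact for someone who leaves early, so that person may have no HADS after baseline. Any HADS count needs a stated denominator.

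**The case against.** The strongest reply is that the plan does not restrict safety reporting to the quoted question. SAP 5.2 first says without limit of type that adverse events are reported at each meeting, and it never calls the prompt the sole source. The platform accepts any adverse event. A change in medical status can be read to include mental health. The interview asks about feelings and reactions, HADS and perceived stress are measured three times, and SAP 9 plans a figure of individual data, where a worsening participant in the analysed set could be seen.

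All of this stands. A reader might infer that the named harms cannot appear in the safety results, or that the study never asks about distress. The documents support neither inference. What the reply does not supply is the link: it shows that information may be collected, not that it will be counted as safety information.

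Three further points stand in part.

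- The protocol ties unease to survey and interview questions, not to the program's exercises. Asking about exercises as well is my extension. It is prompted by Appendix 1, where participants are asked to find positive opportunities in an impairment.
- A participant may not know of a privacy breach, so a yes/no item detects only perceived concerns.
- A zero count in a group of about 10 would be imprecise however the question was worded. That is a matter of sample size and says nothing for or against the wording.

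A figure is missing from the available text under Safety outcomes. It may be the flow chart, and its content could not be checked.

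**Conclusion.** The point holds in a limited form. The only prompted adverse-event question does not ask about the two risks the protocol names, and nothing brings interview distress, recorded difficulties, or HADS and inconvenience referrals into the safety results. For those harms, a finding of no adverse events would rest largely on unprompted reporting.

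No numerical size can be attached, because the documents give no frequency for these harms and no basis for assuming one. The conclusion rests on two assumptions: that the missing figure contains no further safety procedure, and that the general sentence on descriptive statistics does not define what counts as an adverse event. In a small pilot with risks described as minimal, this is a cheap gain in harm ascertainment. It does not affect the usability aims or the endpoint analyses.

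**What to change.** 1. Add two yes/no items to the post-intervention and 1-month REDCap forms: whether any question or exercise caused upset or unease, and whether the participant had any privacy concern. On the 1-month form they also support the Day 52 check in Table 1 without needing a meeting.

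2. State in SAP 5.2 which recorded sources feed the safety results: answers to the prompt, the two new items, platform and telephone reports, recorded difficulties, and distress voiced at interview.

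3. From HADS data already collected, count the participants who were at or below the protocol's existing referral cut on a subscale at baseline and above it at a later visit. Use safety-population participants with a post-baseline HADS, and give that denominator. The cut and the referral stay as they are. With no control group the count is descriptive and does not attribute worsening to the program.

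4. Add one safety table to SAP section 10, by group (stroke survivors, caregivers), showing adverse events, the two items, recorded difficulties and the HADS count.

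The cost is about a minute of participant time at each of two assessments, and one table.
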